### 5.4 Rationale for Selection of Dose, Regimen, and Treatment Duration

Sunitinib has an indication for the treatment of advanced RCC. The FDA-approved dose of sunitinib for advanced RCC is one 50 mg oral dose taken once daily, on a treatment schedule of 4 weeks on followed by 2 weeks off (schedule 4/2), which is the dose that will be used in **Arm A** for this study.

Sunitinib packaging (4/2015) states, "In patients with advanced RCC who are unable to tolerate Schedule 4/2, consider the dose reduction described in the FDA-approved label or, as an alternative, consider modifying the schedule to 2 weeks on treatment followed by 1 week off (Schedule 2/1) using the same dose.

—"Studies supporting Schedule 2/1 have not been reviewed by the FDA. For most studies, the patient population was small and/or analysis was post hoc, and therefore susceptible to bias. The efficacy of any particular alternative dosing schedule has not been established."

<https://www.pfizerpro.com/product/sutent/advanced-rcc/dosing#dm>

Schedule 2/1 will be used in **Arm B** for this study. **Note:** The dose intensity for a 6-week period is the same for schedule 4/2 and 2/1 (50 mg/day \* 28 days = 1400 mg).

### 5.5 Rationale for Study Evaluations

#### PRIMARY PHYSIOLOGICAL DETERMINANTS OF VO2peak

**Rest and Exercise Left Ventricular Ejection Fraction and Cardiac Function** will be measured by 2-D and 3-D echocardiography including Global Longitudinal Strain as described previously. The rate of cardiac dysfunction was approximately 11% in a recent large randomized trial of sunitinib in which schedule 4/2 was utilized. However, to date, testing for cardiac dysfunction in clinical trials has only been performed at rest. We hypothesize that the addition of stress echocardiography will reveal other abnormalities.

**Muscle Function** will be evaluated by two outcomes: (1) upper and lower extremity maximal muscular strength will be assessed as a voluntary one-repetition maximum (1-RM) and muscular endurance (number of repetitions to fatigue at 70% of 1-RM); and (2) muscle cross-sectional area (CSA) of the major muscles near L3 will be assessed using standard of care restaging computed tomography (CT) scans and Slice-O-Matic software (TomoVision; Magog, Canada), as described previously. Standard-of-care CT scans at baseline and after 12 weeks will be used for the muscle CSA analysis. Sarcopenia, reflected as loss of muscle CSA, is known both to predict toxicity from and to develop on VEGF receptor TKI therapy. Therefore, sarcopenia may contribute to decline in cardiopulmonary function.

## PHYSICAL FUNCTIONING/FUNCTIONAL CAPACITY

**Chair-Stand Test** provides a reliable and valid indicator of functional performance of lower body strength in generally active, community-dwelling older adults. Jones et al. examined the test-retest reliability and construct validity of the 30-second chair stand as a measure of lower body strength in 70 adults over 60 years of age (in comparison to a two maximum leg press test). There was a high correlation between chair-stand performance and maximum weight-adjusted, leg-press performance for both men and women ( $r = .78$  and  $.71$ , respectively) supporting the criterion-related validity of the chair stand as a measure of lower body strength. Chair-Stand Test performance decreased significantly across age groups in decades - from the 60s to the 70s to the 80s - and was significantly lower for participants reporting low levels of exercise behavior compared to participants reporting higher levels of exercise behavior. To date, the Chair-Stand Test has not been assessed in patients with mRCC. However, this test, in combination with the Timed Get Up and Go and 6MWD, is widely established as the gold standard for assessment of functional performance in older adults and will complement the performance-based primary outcome of cardiopulmonary function ( $VO_{2\text{peak}}$ ).

**Timed Up and Go** is field-based test that assesses a person's mobility. Specifically, the TUG measures the time that a person takes to rise from a chair, walk three meters, turn around, walk back to the chair, and sit down. This test has been found to be feasible in the majority of older adults. Scores of 10 seconds or less indicate normal mobility, 11 – 20 seconds are within normal limits for frail, elderly, and disabled subjects, and greater than 20 seconds suggests that further examination is required. To indicate normal vs. below-normal performance, a recommended, practical cut-off value for the TUG is 12 seconds. TUG performance decreases with the presence of mobility impairments. To our knowledge, the TUG test has not been assessed in patients with mRCC. This test, in combination with other functional performance measures, is widely established as the gold standard for assessment of functional performance in older adults and will complement the performance-based primary outcome of cardiopulmonary function ( $VO_{2\text{peak}}$ ).

**6-Minute Walk Distance (6MWD):** Six-minute walk testing (6MWT) is a simple, clinically feasible, and objective assessment of functional capacity that is practical even in severely deconditioned clinical populations (e.g., chronic heart failure, chronic obstructive pulmonary disease (COPD), and organ transplant recipients). 6MWT is a robust predictor of mortality in non-cancer settings; only three studies to date have investigated the prognostic importance of 6MWT in the oncology setting.

Specifically, Kasymjanova et al. investigated the association between 6MWD and survival in 64 subjects with inoperable non-small cell lung cancer (NSCLC). Relative to  $<400$  m, a 6MWD  $\geq 400$  m was associated with a 56% reduction in the risk of death after adjustment for important covariates. Similarly, in recent work among 118 subjects with histologically confirmed metastatic NSCLC, Jones et al. found that compared with subjects achieving a 6MWD  $<358.5$  m, the adjusted hazard ratio (HR) for all-cause mortality was 0.61 (95% CI, 0.34 to 1.07) for a 6MWD of 358.5 – 450 m, and 0.48 (95% CI, 0.24 to 0.93) for a 6MWD  $>450$  m. Interestingly, further work by the same group demonstrated that 6MWD was not an independent predictor of prognosis in 243 subjects with grade III/IV recurrent malignant glioma, suggesting that 6MWD may not be an appropriate clinical tool for objectively assessing physical functioning in all cancer populations.

## PATIENT REPORTED OUTCOMES END POINTS (FACIT-F, FKSI-19, Godin Leisure Time Exercise Questionnaire)

Sunitinib treatment causes fatigue and worse QOL; however, the changes that occur with sunitinib on schedule 2/1 and 4/2 have not been prospectively described. Therefore, we propose to describe the changes that occur in this setting.

Because fatigue is a patient reported outcome (PRO) of interest, we will evaluate it using the Functional Assessment of Chronic Illness Therapy – Fatigue (FACIT-F) questionnaire. The FACIT-F measures severity and impact of fatigue on functioning and health-related quality of life (HRQL) experienced in past seven days [Cella, 2002]. It has been used previously to evaluate fatigue with anti-angiogenesis treatments, including assessments for sunitinib [Motzer, 2005; Beaumont, 2006; Motzer, 2013]. The Functional Assessment of Cancer Therapy-Kidney Symptom Index -19 (FKSI-19) is a disease-specific measure that measures disease and

treatment-related symptoms specifically in renal cancer patients [Rosenbloom, 2007; Rosenbloom, 2008; Rao, 2008]. It includes patient self-reports on experience of symptoms in the past seven days such as lack of energy, pain, bone pain, shortness of breath, fatigue, blood in urine, etc. Fksi-19 has been used in a contemporary trial of sunitinib in mRCC. Finally, because it will be important for interpretation of our data to understand activity levels in both arms, we will evaluate leisure time exercise habits with the simple Godin Leisure Time Exercise Questionnaire.

### **DEPRESSION (HADS)**

Depression will be evaluated as described previously using the Hospital Anxiety and Depression Scale (HADS). Fatigue may be difficult to distinguish versus depression in patients with cancer. Understanding the prevalence of depression is necessary to evaluate the FACIT-Fatigue and other related measures because there are high, positive correlations between fatigue and depression.

### **EXPLORATORY ENDPOINTS**

Blood for use in the **plasma angiome multiplex ELISA** will be collected at the same time points as the cardiopulmonary function studies for correlation with primary and secondary endpoints as described previously. Samples will be processed in the Phase I Biomarker Laboratory at Duke (Director: [name]), Molecular Reference Laboratory for the Alliance Oncology Cooperative Group, a national clinical trial research group sponsored by the National Cancer Institute. In cancer patients on therapy, circulating angiogenic factors may be modulated by exercise training during systemic therapy. Therefore, angiogenic biomarker signatures may also predict changes in exercise capacity with therapy.

**Changes in Daily Physical Activity** will be recorded in a subset of patients (up to 16 total, on either arm) using Bluetooth-enabled fitness trackers (Garmin Ltd) paired with the patients' smartphones. Physical activity will be reported in steps per day. This will allow real-time continuous evaluation of a measure of physical functioning that could be scalable to outpatient oncology clinics. We have shown the feasibility of transferring daily step counts from the patient's device to the investigator through setting up an on-line account with a data transferring service known as Self-Generated Health Information exchange (SGHix, <https://sghix.org>) in a previously IRB approved protocol (Duke Pro00063108, unpublished data).

Self-Generated Health Information Exchange (SGHix) is a web based health information platform (<https://app.sghix.org/>), developed and managed by Promantus Inc., which specializes in providing a service for patients to set up an account where they can securely integrate their own health data into one platform. Patients can decide who, including their physicians, has access to their own patient generated health data. Access to data can be turned on and off by the patient through this web service. SGHix was selected as it gives patients the privacy to determine how and when others have access to their patient data.

**Changes in Blood Pressure** will also be recorded in the same subset of patients using Bluetooth-enabled blood pressure cuffs (iHealth, Inc.) paired with the patients' smartphones. Blood pressure will be reported in mmHg on a daily basis. This will allow real-time continuous evaluation of BP, which is both a pharmacodynamic marker of benefit and a key toxicity that may contribute to declines in VO2peak. Blood pressure data will also be transferred through SGHix as detailed in the previous paragraph.

### **5.6 Definition of Evaluable Subjects**

For the primary analysis of change in VO2peak, patients with measurements at baseline and after 12 weeks are evaluable.

### **5.7 Early Study Termination**

This study can be terminated at any time for any reason by the Duke PI-sponsor. If this occurs, all subjects on study should be notified by the appropriate study personnel as soon as possible. Additional procedures

and/or follow up should occur in accordance with **Section 8.8, Early Withdrawal of Subject(s)**, which describes procedures and process for prematurely withdrawn subjects.

## 6 STUDY DRUG: SUNITINIB

[figure not shown]
### 6.1 Names, Classification, and Mechanism of Action

Sunitinib (Sutent®) is a small molecule that inhibits multiple receptor tyrosine kinases (RTKs), including platelet-derived growth factor receptors (PDGFR $\alpha$  and PDGFR $\beta$ ), vascular endothelial growth factor receptors (VEGFR1, VEGFR2, and VEGFR3), stem cell factor receptor (KIT), Fms-like tyrosine kinase-3 (FLT3), colony-stimulating factor receptor Type 1 (CSF-1R), and the glial cell line-derived neurotrophic factor receptor (RET).

### 6.2 Packaging and Labeling

SUTENT, an oral multi-kinase inhibitor, is the malate salt of sunitinib. Sunitinib malate is described chemically as Butanedioic acid, hydroxy-, (2S)-, compound with N-[2-(diethylamino)ethyl]-5-[(Z)-(5-fluoro-1,2-dihydro-2-oxo-3H-indol-3-ylidene)methyl]-2,4-dimethyl-1H-pyrrole-3-carboxamide (1:1). The molecular formula is C22H27FN4O2 · C4H6O5, and the molecular weight is 532.6 Daltons.

The chemical structure of sunitinib malate is:

Sunitinib malate is a yellow to orange powder with a pKa of 8.95. The solubility of sunitinib malate in aqueous media over the range pH 1.2 to pH 6.8 is in excess of 25 mg/mL. The log of the distribution coefficient (octanol/water) at pH 7 is 5.2.

SUTENT (sunitinib malate) capsules are supplied as printed hard-shell capsules containing sunitinib malate equivalent to 12.5 mg, 25 mg, 37.5 mg, or 50 mg of sunitinib together with mannitol, croscarmellose sodium, povidone (K-25), and magnesium stearate as inactive ingredients.

The orange gelatin capsule shells contain titanium dioxide and red iron oxide. The caramel gelatin capsule shells contain titanium dioxide, red iron oxide, yellow iron oxide, and black iron oxide. The yellow gelatin capsule shells contain titanium dioxide and yellow iron oxide. The white printing ink contains shellac, propylene glycol, sodium hydroxide, povidone, and titanium dioxide. The black printing ink contains shellac, propylene glycol, potassium hydroxide, and black iron oxide.

See the sunitinib package insert for full details:

<http://www.labeling.pfizer.com>ShowLabeling.aspx?id=607#S7.1>

## 6.3 Supply, Receipt, and Storage

No study drug (i.e., sunitinib) is being provided by the study. Investigators are responsible for ensuring subjects receive commercially available supplies of sunitinib for the entire duration of study participation.

## 6.4 Dispensing

Not applicable

## 6.5 Compliance, Accountability, Reconciliation, and Return

Not applicable

# 7 SUBJECT ELIGIBILITY

## 7.1 Inclusion Criteria

1. Age  $\geq$  18 years.
2. Histologically confirmed renal cell carcinoma (RCC)
3. One of the two following populations:
  - a. High risk for recurrence of RCC after nephrectomy, in the opinion of the investigator, *OR*
  - b. Locally advanced, unresectable *or* metastatic disease, in the opinion of the investigator, and good or intermediate risk by IDMC Heng Criteria (see **Appendix I**).
4. Karnofsky Performance Status (KPS)  $\geq$  80 (see **Appendix A**)
5. Appropriate for treatment with sunitinib in the opinion of the treating physician.
6. Able to swallow sunitinib and comply with study requirements.
7. Able to walk and jog on a treadmill, in the opinion of the treating physician.
8. Must be able to complete an acceptable cardiopulmonary exercise test (CPET) at baseline defined as at least one of the following:
  - Achieving a plateau in oxygen consumption concurrent with an increase in power output;
  - Respiratory exchange ratio  $\geq$  1.1 (RER);
  - Volitional exhaustion with a rating of perceived exertion  $\geq$  17 (RPE).
9. Subjects must have normal organ and marrow function as defined below:
  - Absolute neutrophil count  $\geq$  1,200/ $\mu$ L
  - Hemoglobin  $\geq$  9 g/dL
  - Platelets  $\geq$  75,000/ $\mu$ L
  - Total bilirubin  $\leq$  1.5 x institutional upper limit of normal
  - AST(SGOT)/ALT(SGPT)  $<$  2.5 x institutional upper limit of normal
  - Urine protein creatinine (UPC) ratio of  $<$  1 (see **Appendix G** schedule of events footnote)
  - Creatinine  $\leq$  2.0 OR creatinine clearance  $>$  30 mL/min/1.73 m^2 for subjects with creatinine levels above institutional normal (see **Appendix H**).
  - Left ventricular ejection fraction (LVEF)  $\geq$  lower limit of institutional normal as assessed by echocardiography.
10. For the sixteen patients who elect to participate in the optional technology portion involving electronic step counts and blood pressure monitoring, the patient must have a Bluetooth-enabled smart phone, which is compatible with the wireless health monitors.
11. For women of childbearing potential (WOCBP) must have a negative serum pregnancy test prior to the start of the study. Women of childbearing potential (WOCBP) must agree to follow instructions for method(s) of contraception for the duration of the study. Medically acceptable contraceptives include: (1) surgical sterilization (such as a tubal ligation or hysterectomy), (2) approved hormonal contraceptives (such as birth control pills, patches, implants or injections), (3) barrier methods (such as a condom or diaphragm) used with a spermicide, or (4) an intrauterine device (IUD). Contraceptive measures such as Plan B (TM), sold for emergency use after unprotected sex, are not acceptable methods for routine use. If you do become pregnant during this study or if you have unprotected sex, you must inform your study physician immediately.

12. For men who are sexually active, must agree to use a two medically acceptable forms of birth control (one of which must include a condom as a barrier method of contraception) in order to be in this study. Medically acceptable contraceptives include: (1) surgical sterilization (such as a vasectomy), or (2) a condom used with a spermicide. Contraceptive measures such as Plan B (TM), sold for emergency use after unprotected sex, are not acceptable methods for routine use. Men must also agree to inform their partner of the potential for harm to an unborn child. She should know that if pregnancy occurs, the subject will need to report it to the study doctor, and she should promptly notify her doctor. The study doctor will ask if the subject's partner is willing to provide updates on the progress of the pregnancy and its outcome. If the subject's partner agrees, this information will be provided to Pfizer, Inc. for safety monitoring follow-up.

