**TABLE 3. SCHEDULE OF EVENTS**

Phase		Screening	Exercise Testing A c,d	Exercise Testing B and Randomization c	Treatment Period			End of Treatment Visit	Unscheduled Visit a
Day		-84 to -1	-4	-2/-1	1	4/2: 29 2/1: 36	85	NA	NA
Week		-12 to -1			1	4/2: 4 2/1: 5	13	See Note	NA
Window (Days)		NA	-28 to -1	-28 to -1	NA d	±3	±3	±7	NA
General Evaluations	See Section								
Informed Consent b	8.1.1.1	X							
Eligibility Criteria	7	X							
Medical History	8.9.1	X							
Randomization c	8.3			X c					
Physical Exam e	8.9.2	X	X		X o	X	X	X	X
Height, Weight, BMI n	8.9.2	X	X		X o	X	X	X	X
Vital Signs f	8.9.2	X	X		X o	X	X	X	X
Performance Status g	App. A	X	X		X o	X	X	X	X
Concomitant Medications	5.3.2	X	X		X o	X	X	X	X
Adverse Events h	9.1	X	X	x	X o	X	X	X	X
Laboratory Evaluations									
CBC with Platelets	8.1-8.6	X	X		X o	X	X	X	X i
Serum Chemistry	8.1-8.6	X	X		X o	X	X	X	X i
Thyroid Function j	8.1-8.6	X				X	X		
UPC k	App. G	X	X		X o	X	X	X	X i
Serum Pregnancy Test (WOCBP Only)		X							
Echo	8.1	X							
Disease Evaluations									
CT Chest, Abdomen, Pelvis		X i					X		
Bone Scan (opt.)		X i							
Objective Evaluations									
CPET	8.9.3		X			X	X		
Rest and Exercise 2-D + 3-D Echo	8.9.3		X				X		
Muscular Strength/Muscular Endurance m	8.9.3			X		X	X		
Muscle CSA l	8.9.3		X				X		
Chair Stand	8.9.3			X		X	X		
Timed Up and Go	8.9.3			X		X	X		
6 min walk distance	8.9.3			X		X	X		
FACIT-Fatigue	App. B		X			X	X		
FKSI-19	App. C		X			X	X		
Godin Leisure	App. D		X			X	X		

HADS	App. E		X			X	X		
Drug Diary p					X	X	X	X	X
Plasma Angiome Multiplex ELISA	8.9.3		X				X		
Step Counts	8.9.3		X			X	X		
Blood Pressure	8.9.3		X			X	X		
Treatment									
Sunitinib 4/2	5.1				X	X	X		
Sunitinib 2/1	5.1				X	X	X		

**Note:** The End-of-Treatment Visit will occur approximately 30 days after the last dose of sunitinib or on Day 85, whichever occurs first.

- a. Unscheduled visits may be performed at any time during the study as clinically indicated to assess for or follow-up on AEs. Unscheduled visits may also occur due to holidays or other scheduling difficulties.

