- b. Informed consent may be performed within 84 days prior to enrollment (Day 1), but it must be obtained prior to the performance of any study-specific procedures.
- c. Randomization should be performed after baseline testing (specifically, CPET) is completed from day -28 to -1, but only after eligibility is confirmed. Note that the Baseline Exercise Testing Visits are structured to take place over 1-2 consecutive days. **See also footnote d. below.**
- d. Day 1 is defined as the day the patient begins taking sunitinib. Because day 1 is defined by this activity, there is no window. The day 1 Physical Exam, Weight, BMI, Vital Signs, PS, Con Meds, AEs, and labs have a  $\pm 3$  day window.
- e. A complete physical examination is required at the Screening, Exercise Testing Day A, Day 29-36, and Day 85 visits. A brief symptom-directed physical examination should be performed at all other clinic visits.
- f. Vital signs (temperature, blood pressure, heart rate) are to be obtained at each visit. SpO2 collected at baseline.
- g. Performance status measured by KPS (as part of IDMC) (see **Appendix A**) at screening. KPS will be used throughout the remainder of the study.
- h. All non-serious adverse events will be collected from the time of first dose of study drug until the End of Treatment Visit. Serious adverse events that are related to study procedures are recorded from the time the informed consent form is signed until the End of Treatment Visit (or screen failure). In the event of no End of Treatment Visit, adverse event information will be collected through 30 days after the last dose of study drug. Subjects should be contacted by phone for adverse event follow-up if they do not come to the clinic for the End of Treatment Visit.
- i. Clinical laboratory tests may be performed at unscheduled visits if clinically indicated.
- j. Thyroid function tests (TFTs) should include TSH and free T4.
- k. If UPC  $\geq 1$  (see **Appendix G**) at the baseline/ screening assessment, then a 24-hour urine protein must be assessed. Subjects must have a 24-hour urine protein value  $< 1$  g to be eligible.

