- l. Computed tomography (CT) chest, abdomen, and pelvis should be performed at the time of screening and after 12 weeks (at day 1 of week 13). PET/CT is allowed but should be performed at both timepoints for consistency. Muscle CSA will be calculated from these scans. Scans may be used to calculate Muscle CSA if they were collected within the window for collection of that scan, Bone scan is optional, based on clinical suspicion at baseline.
- m. Muscular Strength and Muscular Endurance must be done at least 24 hours before or after CPET to allow adequate recovery time.
- n. Height is only required to be collected at screening.
- o. Physical Exam, Weight, BMI, Vital Signs, PS, Con Meds, AEs, and labs do not need to be repeated if performed within 14 days of day 1.
- p. Drug Diary given to subject on Treatment Day 1. Drug Diary collected on all other visits.

BMI, body mass index; KPS, Karnofsky Performance Status; CBC, complete blood count; CT, computed tomography; opt., optional; CPET, cardiopulmonary exercise test; ; CSA, cross-sectional area; FACIT, Functional Assessment of Chronic Illness Therapy; FCSI-19, Functional Assessment of Cancer Therapy-Kidney Symptom Index-19.

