## 8.1 Screening Examination

The screening examination will take place between Day -84 and -1. The subject must sign an Informed Consent before any screening procedure takes place. Subject data to be collected at the Screening Examination includes:

- Informed Consent
- Eligibility Criteria
- Medical History
- Physical Exam
- Height, Weight, BMI
- Vital Signs
- Performance Status (KPS)
- Concomitant Medications
- Adverse Events (baseline symptoms)

- CBC with Platelets (hemoglobin, hematocrit, platelet count, white blood cell count, total [absolute] neutrophils)
- Serum Chemistry (sodium, potassium, chloride, total CO2 [bicarbonate], calcium, BUN, creatinine, glucose, albumin, total bilirubin, total protein, alkaline phosphatase, AST, ALT)
- Thyroid function (TSH and free T4)
- UPC (see **Appendix G**)
- Serum pregnancy test
- Echo
- CT chest, abdomen, and pelvis
- Bone scan (optional; if subject has known bone metastases then bone scan is required)

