### 8.3 Randomization

Subjects will be randomized after inclusion/exclusion criteria are met, exercise testing is complete and subject has completed an acceptable CPET and Muscular Strength. Exercise Testing Day B and Randomization may occur on the same day if eligibility is confirmed prior to randomization. Randomization and related activities can occur between days -28 to -1.

### 8.4 Treatment Period: Day 1

Day 1 is defined as the day on which the subject begins taking sunitinib.

**Note:** Subjects should start treatment with sunitinib according to the schedule to which they are randomized.

Examinations include:

- Physical Exam
- Weight, BMI
- Vital Signs
- Performance Status (KPS)
- Concomitant Medications
- Adverse Events
- CBC with Platelets (hemoglobin, hematocrit, platelet count, white blood cell count, total [absolute] neutrophils)
- Serum Chemistry (sodium, potassium, chloride, total CO2 [bicarbonate], calcium, BUN, creatinine, glucose, albumin, total bilirubin, total protein, alkaline phosphatase, AST, ALT)
- UPC (see **Appendix G**)
- Note: Many of these activities do not need to be repeated if they are performed within 14 days of day 1 (see **Schedule of Events**).
- Drug diary (give to subject)

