### **9.3 Procedure in Case of Pregnancy**

Sunitinib is Pregnancy Category D.

Sunitinib can cause fetal harm when administered to a pregnant woman. As angiogenesis is a critical component of embryonic and fetal development, inhibition of angiogenesis following administration of sunitinib should be expected to result in adverse effects on pregnancy. In animal reproductive studies in rats and rabbits, sunitinib was teratogenic, embryotoxic, and fetotoxic.

Subjects receiving sunitinib are advised to use 2 acceptable methods of birth control (one of which must include a condom as a barrier method of contraception) starting at the time of screening and continuing throughout the course of treatment and for at least three months after sunitinib is discontinued.

If, during the conduct of the clinical trial, a male subject impregnates his partner, OR a female subject becomes pregnant, the subject should report the pregnancy to the Investigator. With the permission of the pregnant partner, the Investigator should report the pregnancy to Pfizer as an SAE within 24 hours of awareness of the event. The expected date of delivery or expected date of the end of the pregnancy, last menstruation, estimated fertility date, pregnancy result, and neonatal data, etc., should be included in this information.

With the permission of the pregnant partner, the Investigator should report the outcome of the pregnancy (independent of outcome, e.g., full-term delivery, pre-term delivery, spontaneous abortion, induced abortion, stillbirth, death of newborn, congenital anomaly [including anomaly in a miscarried fetus, etc.]) in accordance with the same reporting procedure as for SAEs (see **Section 9.2.1**). The date of outcome of the pregnancy,

gestational age, date of birth, and neonatal data, etc., should be included in this information. Informed consent will need to be obtained from the pregnant partner to document her permission to disclose this information to Pfizer.

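### The serum pregnancy test is not tied to the first dose: the only scheduled test is at Screening, so a result up to 84 days old satisfies the plan

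*Combined protocol and SAP*

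**What the plan says.** Under inclusion criterion 11 (Section 7.1), women of childbearing potential "must have a negative serum pregnancy test prior to the start of the study". The criterion sets no maximum age for the result, does not mention the first dose, and leaves the start of the study undefined: it could be consent, registration, randomization or Day 1.

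Table 3 marks the test in the Screening column only. Section 8.1 is the only visit list with the entry "Serum pregnancy test", and it states: "The screening examination will take place between Day -84 and -1". Section 8.4 fixes the first dose: "Day 1 is defined as the day on which the subject begins taking sunitinib".

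For routine laboratory work, Table 3 footnote o waives the Day 1 repeat only for recent results: "labs do not need to be repeated if performed within 14 days of day 1".

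On the hazard, Section 9.3 says that sunitinib can harm the fetus of a treated woman, and reports: "In animal reproductive studies in rats and rabbits, sunitinib was teratogenic, embryotoxic, and fetotoxic". The same section advises two birth-control methods from screening onward. Criterion 11 requires agreement to contraception and immediate notice to the study physician of a pregnancy or of unprotected sex.

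**The concern.** The criterion exists to prevent fetal exposure to sunitinib, so the status that matters is the one on the day the drug is started. A single test early in a 12-week window cannot show a conception that follows it, and may miss a very early pregnancy on the day it is taken. A woman in either position would meet criterion 11 and Table 3 as written and could start treatment, with no later test required to show it.

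The trial supplies no drug: Section 6.3 relies on commercial stock, and Sections 6.4 and 6.5 mark dispensing and accountability as not applicable. So no dispensing step within the trial exists at which a current result would be checked. A pregnancy in a subject is to be reported to the manufacturer as an SAE within 24 hours (Section 9.3), but that acts after exposure.

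**Working it through.** **1. The longest permitted gap.** Inputs: Screening from Day -84 to Day -1 (Section 8.1, Table 3); first dose on Day 1 (Section 8.4).

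- 84 days / 7 = 12 weeks, which reproduces the Week -12 entry in Table 3.
- Table 3 footnote b also counts 84 days back from Day 1, for consent.
- Age of the only scheduled test at first dose: at most 84 days, at least 1 day.

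**2. Where laboratory tests that bear on eligibility are scheduled before dosing.**

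| Test | Screening | Exercise Testing A | Day 1 |
|---|---|---|---|
| CBC, chemistry, urine protein-creatinine ratio | yes | yes | yes, unless done within 14 days |
| Serum pregnancy test | yes | no | no |

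The lists in Sections 8.2, 8.4, 8.5 and 8.6 agree with Table 3: none includes the pregnancy test. Scheduled pregnancy tests after Screening: 0.

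**3. A like-for-like comparison.** The 14 days in footnote o is not a guaranteed pre-dose limit, because footnote d gives the Day 1 labs a window of 3 days either side, so they may be drawn after the first dose. The draw that must precede dosing is Exercise Testing A, confined to Day -28 to -1.

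- Oldest permitted pre-dose CBC, chemistry or urine ratio: 28 days.
- Oldest permitted pregnancy test: 84 days, which is 84 / 28 = 3 times as long, or 84 - 28 = 56 days longer.
- Against the 14 days of footnote o: 84 / 14 = 6 times as long.

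**4. What a repeat would achieve.**

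- Repeat at Exercise Testing A: the maximum age falls from 84 to 28 days, with no new visit or draw.
- Repeat with the Day 1 labs, when these are drawn before dosing: the age falls to at most 3 days.
- If the sponsor adopted 14 days, existing draws would not always serve. With Exercise Testing A on Day -20 and the Day 1 labs two days after the first dose, no scheduled draw falls in the 14 days before dosing, and one would have to be moved forward.

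**5. Interaction with randomization.** Randomization may take place from Day -28, but only once eligibility is confirmed (Section 8.3, Table 3 footnote c). If the only test lay within 14 days of dosing, a patient randomized between Day -28 and Day -15 would not yet have confirmed eligibility. The screening test therefore has to stay, and the repeat should be a condition for starting the drug.

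**The case against.** The strongest reply is that the interval is not unprotected. Section 9.3 advises two contraceptive methods from screening, and criterion 11 requires agreement to contraception and prompt reporting. For a conception after Screening to reach dosing, contraception must fail or go unused, and the pregnancy must go unrecognised or unreported. This stands as mitigation, and a reader who infers that the plan offers no safeguard would be wrong. It does not replace a test, because nothing verifies status before dosing. The safeguards also differ: criterion 11 lists acceptable methods for women without asking for two, for the duration of the study, whereas Section 9.3 advises two including a condom, until at least three months after sunitinib ends. Those passages must be reconciled.

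Other replies also limit the point:

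- A reader might infer that the pregnancy test alone is left unrefreshed. It is not: thyroid function is measured at Screening and not again until Day 29 or 36. Thyroid function, however, is not an eligibility criterion.
- 84 days is the outer limit. A site may test as late as Day -1, and the documents give no typical interval.
- The 14 days in footnote o waives repeats of routine assessments. It is not a standard for pregnancy testing, and a recent test can still miss a very early pregnancy.
- A reader might infer that an exposed pregnancy would cost the patient's Day 85 evaluation. The documents do not say so, and the point does not need it.
- Sites may retest as ordinary practice. Perhaps, but the protocol does not require it.

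**Conclusion.** The point holds in a limited form. Inclusion criterion 11 and Table 3 do not link the pregnancy test to the first dose, and a negative result up to 84 days old satisfies the plan. That is three times the 28-day limit that Exercise Testing A places on the other laboratory eligibility tests before dosing. Contraception and reporting lower the risk but do not close the gap.

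The number of women concerned is unknown. Planned accrual is 36 in all (Section 11.6), and the share of childbearing potential is not given; it is assumed to be small. The estimate of change in VO2peak is not at issue. This is a participant-safety improvement that should be made because the possible harm is serious and the change is cheap. It assumes that no repeat test is required by a document outside the protocol. The documents do not support reading this as a plan without safeguards, or 84 days as the usual delay.

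**What to change.** 1. Keep the screening test in Table 3 and Section 8.1, so that eligibility can be confirmed before randomization.
2. Add to Table 3, and to the lists in Sections 8.2 and 8.4, a repeat serum pregnancy test for women of childbearing potential. Take it at the last scheduled blood draw before Day 1: Exercise Testing A, or the Day 1 labs if these are drawn before dosing. Require a negative result before the first dose; because of the window in footnote d, the requirement must refer to the result and not only to the visit.
3. Reword criterion 11 to refer to the first dose of sunitinib in place of the start of the study, and state the maximum interval. The sponsor sets it; the 14 days of footnote o is one available reference.
4. Reconcile criterion 11, Table 3 and Section 9.3, including their contraception wording.

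Cost: one extra assay in a few women, usually on blood already being drawn, and occasionally a draw moved ahead of Day 1. Rarely, a positive repeat would leave a patient randomized but untreated. Section 5.3.3 already provides for replacing such a patient, and without a week-12 evaluation she would not enter the modified intent-to-treat population used for the primary analysis (Section 11.1).
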